3.2 Justification for Study Design and Population

This study is designed to evaluate the use of Lymphoseek as an ILM and SLNB agent in subjects with known cancer of the cervix by evaluating the FNR for identifying tumor-positive lymph nodes as determined by histopathological evaluation of sentinel and non-sentinel lymph nodes following pelvic lymphadenectomy. In addition, the concordance of detection rates of Lymphoseek and of dyes will be determined.

Pelvic lymphadenectomy, with or without ILM using a dye as the mapping agent, is the current standard of care for patients undergoing cervical tumor resection. Therefore, this study will directly evaluate Lymphoseek's performance relative to the standard of care.

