5.3 Dye Dosage and Administration

A dye, such as Lymphazurin (isosulfan blue 1%) or indocyanine green, may be administered to subjects as part of their standard of care. The injection will be performed as deemed appropriate by the surgeon and in accordance with the standard of care at the clinical site.

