negative or no counts (not hot)	positive (hot)	Comment on why lymph node was removed. Send to pathology for further evaluation.
Dye Status		
dye-identified node	N/A	ANY dye-identified node is sent to pathology for further evaluation regardless of radioactive status.

6. A thorough evaluation of the remaining lymphatic basin should be undertaken since more than one LN may be found. This evaluation should include a combination of palpation, visualization, and gamma detector survey for evidence of dye and/or increased gamma detector count rates.
7. Probing of the area will be complete when all selected node counts are negative by use of the threshold criterion. The surgeon will continue with visualization and palpation according to local practice to ensure that no grossly positive LNs remain at the site of resection.

If a subject has neither a dye-identified node nor any “hot” nodes, continue with visualization and palpation according to your medical expertise.

Pelvic lymphadenectomy will be performed in accordance with institutional standards. Additional surgical intervention such as radical hysterectomy should be performed in accordance with the subject’s surgical plan and the discretion of the surgeon.

All removed LNs (SLNs and NSLNs) must be sent to pathology for using the minimum requirements of histopathological evaluation outlined in the trial pathology manual.

For the purposes of analysis, a sentinel lymph node is defined as being hot ex vivo (lymph nodes with counts above the 3σ rule threshold).

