9.2 Randomization Methods

There is no randomization planned for this study. All enrolled subjects will receive Lymphoseek along with an optional administration of either VBD or ICG.

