9.9 Statistical Analysis

9.9.1 Analysis Populations

The following analysis populations will be defined:

Intent-to-treat (ITT): The ITT population will include all enrolled subjects with administration of test medicine for whom at least one lymph node was removed with histopathology available.

Per protocol (PP): The PP population will include all ITT subjects without major protocol violations.

Safety: The safety population will include all enrolled subjects with administration of test medicine.

The analysis of the efficacy endpoints will be conducted on ITT and PP populations. The primary analysis set will be the ITT analysis set. All safety analyses will be conducted on the safety population.

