Along with reporting the total number of subjects with at least one pathologically positive non-SLN and the observed rate of non-SLN tumor detection, an exact two-sided 95% confidence interval will be computed

The nodal concordance, P_1 , will be computed as follows using lymph nodes from all subjects in the ITT population:

$$P_1 = \frac{\text{Number of SLNs identified intraoperatively by VBD or ICG}}{\text{Number of lymph nodes identified intraoperatively by VBD or ICG}}$$

9.9.4.1 Along with reporting the number of SLNs identified intraoperatively by VBD or ICG and the observed nodal concordance, an exact two-sided 95% confidence interval will be computed.

The subject concordance, P_2 , will be computed as follows using all subjects in the ITT population:

$$P_2 = \frac{\text{Subjects whose lymph nodes that were intraoperatively identified by VBD or ICG were also all identified by Lymphoseek}}{\text{Subjects with at least one lymph node intraoperatively identified by VBD or ICG}}$$

Along with reporting the number of subjects in the numerator and the observed subject concordance, an exact two-sided 95% confidence interval will be computed.

The reverse nodal concordance, P_3 , will be computed as follows using lymph nodes from all subjects in the ITT population:

$$P_3 = \frac{\text{Number of SLNs identified intraoperatively by VBD or ICG}}{\text{Number of SLNs}}$$

Along with reporting the number of SLNs identified intraoperatively by VBD or ICG and the observed reverse nodal concordance, an exact two-sided 95% confidence interval will be computed.

The subject reverse concordance, P_4 , will be computed as follows using all subjects in the ITT population:

$$P_4 = \frac{\text{Subjects whose SLNs were also all identified by VBD or ICG}}{\text{Subjects with at least one SLN}}$$

Along with reporting the number of subjects in the numerator and the observed reverse subject concordance, an exact two-sided 95% confidence interval will be computed.

The average number of SLNs per subject will be computed, along with a 95% confidence interval.

The average number of lymph nodes identified intraoperatively by dye per subject will be computed, along with a 95% confidence interval.

The average number of lymph nodes identified by preoperative Lymphoscintigraphy per subject will be computed, along with a 95% confidence interval.

The number and percent of lymph nodes identified by preoperative Lymphoscintigraphy will be reported per anatomical location.

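### Dye is optional, but reverse concordance (P3, P4) is computed over all ITT subjects, so a subject with an SLN who was given no dye counts as a dye failure and lowers the result

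*Combined protocol and SAP*

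**What the plan says.** Protocol section 9.9.4 defines the two reverse concordance measures.

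- P3, nodal: "The reverse nodal concordance, P_3 , will be computed as follows using lymph nodes from all subjects in the ITT population". The numerator is the SLNs that VBD or ICG also identified; the denominator is all SLNs.
- P4, subject level: "The subject reverse concordance, P_4 , will be computed as follows using all subjects in the ITT population". The numerator is subjects whose SLNs were all dye-identified; the denominator is subjects with one SLN or more.

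The same section adds a mean dye count: "The average number of lymph nodes identified intraoperatively by dye per subject will be computed, along with a 95% confidence interval". No population is named for it, but section 9.9.1 says: "The analysis of the efficacy endpoints will be conducted on ITT and PP populations".

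Four other places determine who falls into these denominators.

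- Section 9.2: "All enrolled subjects will receive Lymphoseek along with an optional administration of either VBD or ICG".
- Section 5.3, on dye: it "may be administered to subjects as part of their standard of care".
- Section 3.2: "Pelvic lymphadenectomy, with or without ILM using a dye as the mapping agent, is the current standard of care".
- Section 8.4.3: "For the purposes of analysis, a sentinel lymph node is defined as being hot ex vivo".

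The ITT definition in 9.9.1 asks for administration of the test medicine and one removed node with histopathology. It sets no condition on dye.

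**The concern.** Reverse concordance is meant to show how often dye also finds the nodes that Lymphoseek finds. A node from a subject who was given no dye says nothing about that. Under the formulas as written, such a node still counts in the denominator, where it looks the same as a node that dye was given for and missed. P3 and P4 then mix two things, how often dye was used and how well it performed, and a reader of the results cannot separate them.

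The error runs one way. Whenever some subjects with an SLN are undyed and some SLNs elsewhere are dye-identified, dye is understated relative to Lymphoseek, the sponsor's product. Reverse concordance is a stated secondary objective (section 2.2) and a listed endpoint (section 9.4.2). No decision rule depends on it.

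**Working it through.** **The plan's own figures.** No expected value or precision is given for P3 or P4. The only computed design figure is the FNR half-width in section 9.7. For 1 of 8 subjects the exact (Clopper-Pearson) 95% interval is 0.3% to 52.7%, so half its width is 26.2%, which reproduces the stated 26%. The intervals below use the same method.

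**Who enters each measure.** Take an ITT subject with at least one SLN who received no dye.

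| Measure | Denominator | In denominator? | Can enter numerator? |
|---|---|---|---|
| P1 | dye-identified nodes | no | no |
| P2 | subjects with a dye-identified node | no | no |
| P3 | all SLNs | yes | no |
| P4 | subjects with an SLN | yes | no |

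P1 and P2 drop her automatically. P3 and P4 do not. An ITT subject with no SLN enters neither P3 nor P4, dyed or not.

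**Size.** Let p be the value among dyed subjects and f the dyed share. For P3, f is the share of SLNs that lie in dyed subjects; for P4, it is the share of subjects with an SLN who were dyed. Then

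reported value = f × p.

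The documents give neither f nor p. The values below are assumptions.

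| f | P3 if p = 80% | P4 if p = 60% |
|---|---|---|
| 100% | 80% | 60% |
| 90% | 72% | 54% |
| 75% | 60% | 45% |
| 50% | 40% | 30% |

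**Illustration in counts.** Assume 40 ITT subjects with 2 SLNs each, of whom 30 are dyed. That gives 80 SLNs, 60 of them in dyed subjects. With p = 80%, 0.80 × 60 = 48 SLNs are dye-identified. With p = 60% for P4, 0.60 × 30 = 18 subjects have all their SLNs dye-identified.

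| Measure | As written (exact 95% CI) | Dyed subjects only (exact 95% CI) |
|---|---|---|
| P3 | 48/80 = 60.0% (48.4 to 70.8) | 48/60 = 80.0% (67.7 to 89.2) |
| P4 | 18/40 = 45.0% (29.3 to 61.5) | 18/30 = 60.0% (40.6 to 77.3) |

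**Mild case.** With 2 of 40 undyed and equal SLN counts, P3 = 0.80 × 38/40 = 76%.

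**Unequal node counts.** Keep 30 of 40 dyed and p = 80%.

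- 3 SLNs per dyed and 2 per undyed subject: f = 90/110 = 0.818 and P3 = 65.5%.
- 2 per dyed and 3 per undyed subject: f = 60/90 = 0.667 and P3 = 53.3%.

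**Mean number of dye-identified nodes.** If it is taken over ITT, as 9.9.1 implies, each undyed subject contributes a zero. The mean is then multiplied by the share of ITT subjects who were dyed.

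**Whether another rule removes these subjects.**

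- Replacement (section 4.4) covers missing study medication, surgery or mapping with biopsy. Absence of dye is not listed.
- The PP repeat in 9.9.4 removes only major protocol violators. Omitting an optional dye is not described as a violation.
- The complete-case rule (section 9.8) does not mention undyed subjects. Section 8.4.3 has the identification method recorded for every node, and a Lymphoseek-only finding is a valid entry. An undyed subject's SLN therefore has a complete record.

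**The case against.** The strongest counter-argument is section 9.8. Where no dye was given, dye identification was never assessed, so an analyst could reasonably treat it as missing and leave the subject out. The objective is worded as a comparison of dye with Lymphoseek, which presupposes that both were given. Dye use may also be close to universal: the synopsis names dye among the injections, and surgeons must have prior mapping experience (section 3.3). Finally, every size quoted rests on assumed inputs, and the endpoints are exploratory.

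Part of this stands. Section 9.8 can be read that way, dye uptake is unknown, and the effect is zero if every subject with an SLN is dyed. The population for the mean is inferred rather than stated. P2's denominator also gives a lower bound on how many subjects were dyed, although undyed subjects remain merged with those in whom dye failed.

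The objection does not remove the problem. The P3 and P4 formulas name their denominators explicitly, and those include undyed subjects. A general missing-data sentence that never mentions dye does not clearly override them, particularly when the node record is complete. At best, two analysts could report different P3 and P4 values from the same data.

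**Conclusion.** The concern holds. As written, P3 and P4 are the true reverse concordance scaled down by the dyed share. The loss is nil at full dye use, 4 points for P3 with 2 of 40 undyed, and 20 points for P3 and 15 for P4 with 10 of 40 undyed. These sizes rest on assumed values of 80% (P3) and 60% (P4) in dyed subjects and on equal SLN counts. The direction does not depend on those assumptions, provided some SLNs are dye-identified. The point about the mean dye count is weaker because its population is inferred. The primary FNR, P1 and P2 are unaffected. This should be fixed, but it does not threaten the trial's main result.

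**What to change.** In section 9.9.4, state that P3, P4 and the mean number of dye-identified nodes per subject are computed in ITT (and, for the repeat, PP) subjects who received VBD or ICG, and report how many subjects that is. Subjects who were dyed but had no stained node stay in, since they are genuine dye failures.

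The cost is one sentence and one subset flag. Dye administration is already an item in the Schedule of Events (Appendix 1). The denominators become smaller, with a modest loss of precision: in the illustration the P4 interval widens from about 32 points (61.5 − 29.3) to about 37 (77.3 − 40.6). If every subject with an SLN turns out to have been dyed, P3 and P4 do not change.

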9.9.5 Safety Analyses

All AEs will be observed for each subject from injection until termination from the study. Additionally, all SAEs will be observed for each subject from time of consent until termination from the study. Prior to analysis, all AEs will be coded using MedDRA. Based on these coded terms, AEs will be summarized using system organ class and preferred term for all subjects in the safety population. AEs will also be summarized by severity, relationship to investigational product, relationship to dye, and relationship to study procedure. All AEs will be listed.

Summary statistics (mean, median, sample size, standard deviation, minimum, and maximum) will be computed on the raw and change from baseline values for each vital sign parameter by timepoint. The pre-injection timepoint will serve as baseline. If there are multiple vital signs taken at any timepoint, then the latest set of vital signs will be used for the analysis. All vital sign data will be listed.

Additional analyses of safety variables for this study may be conducted as described in the Statistical Analysis Plan document.

9.10 Interim Analyses

No formal interim analyses will be conducted during this study.

10 DATA HANDLING AND QUALITY ASSURANCE

10.1 Data Recording

Data required according to this protocol is captured in the subject's source documentation and are to be entered into the eCRFs (provided by the sponsor) as soon as possible.

10.1.1 Electronic CRF design

Electronic data capture with the sponsor's eCRF will be used for collecting all data generated during the study. The eCRF application has a built-in plausibility check system, forcing the investigators to answer the questions in the appropriate manner, and auto-checks for missing data. The system type and eCRF details will be outlined in a separate document that will be provided by the sponsor and maintained in the TMF.

10.2 Monitoring

This study will be monitored regularly by a clinical research associate (CRA) from the sponsor or a contract research organization (CRO). Monitoring procedures include one or more visits designed to clarify all prerequisites before the study starts. Interim monitoring visits will take place on a regular basis according to a schedule fixed by mutual agreement. During these visits, the CRA will check for completion of the entries on the eCRFs, their compliance with the protocol and with GCP, and will compare the eCRF entries with the source data.

All data recorded in the eCRF will be captured in the source documentation.

The CRA will verify the correct use of the investigational product. The investigational product will not be supplied to the investigator site prior to a favorable opinion from the IRB/IEC and the regulatory authority and, if appropriate, from the radiation protection authorities.

In addition, the CRA will determine whether all AEs and SAEs have been appropriately reported (including adherence to the time periods required for SAEs).

10.3 Data Processing

Study data documentation will be maintained specifying all relevant aspects of data processing for the study (including data validation, cleaning, correcting, releasing). This documentation will be stored in the TMF.

For data coding (e.g., AEs, medication, medical/surgical history), internationally recognized and accepted dictionaries will be used. These and the processes used for coding will be specified in the data management plan.

10.4 Auditing

A member of the sponsor's (or a designated CRO) quality assurance unit may arrange to visit the investigator in order to audit the performance of the study at the study site and the study documents originating there. The auditor(s) will usually be accompanied by a CRA or the study team lead. The investigator will be informed about the outcome of the audit.

In addition, inspections by health authority representatives and IEC(s)/IRB(s) are possible at any time. The investigator is to notify the sponsor of any such inspection immediately.

10.5 Archiving

Essential documents shall be archived safely and securely in such a way that ensures that they are readily available upon authorities' request.

Patient (hospital) files will be archived according to local regulations and in accordance with the maximum period of time permitted by the hospital, institution, or private practice. Where the archiving procedures do not meet the minimum timelines required by the sponsor, alternative arrangements must be made to ensure the availability of the source documents for the required period.

The investigator/institution notifies the sponsor if the archival arrangements change (e.g., relocation or transfer of ownership).

The investigator site file is not to be destroyed without the sponsor's approval.

The investigator's contract will contain all regulations relevant for the study center.

10.6 Premature Termination of the Study

Termination by the Sponsor

The sponsor may terminate the study at a site any time for any of the following reasons:

1. Failure to enroll subjects
2. Protocol violations
3. Inaccurate or incomplete data
4. Unsafe or unethical practices
5. Questionable safety of the investigational product
6. Suspected lack of efficacy of the investigational product
7. Administrative decision

Termination by the Investigator

If the Investigator terminates the study prematurely, the Investigator must do the following:

- Return all unused investigational products and related study materials to the sponsor.
- Provide the IRB/IEC and the sponsor with a written statement describing why the study was terminated prematurely. Prompt compliance with this requirement is essential so that the sponsor may comply with its regulatory obligations.

10.6.1 Study as a Whole

The sponsor retains the right to prematurely terminate the study as a whole at any time.

At the discretion of the sponsor, the entire study may be canceled for medical reasons (e.g. unanticipated adverse events). In addition, the sponsor retains the right to end the study at any time if the study cannot be conducted as specified in the protocol.

In case of premature termination or suspension of the study, the principal investigator/sponsor will promptly inform the investigator/institutions, regulatory authorities, and IRB/IEC of the termination or suspension and the reason for that.

10.6.2 Study Participant

Individual subjects may be withdrawn from the study according to the criteria specified in [Section 4.3](#).

11 ETHICAL AND LEGAL ASPECTS

11.1 Ethical and Legal Conduct of the Study

The planning and conduct of this clinical study are subject to national laws. Only when all of the requirements of the appropriate regulatory authority have been fulfilled will the study begin. The study will be conducted in accordance with the ethical principles that have their origin in the Declaration of Helsinki and the ICH-GCP Guidelines of 17 Jan 1997. At the discretion of the investigator, the entire study may be canceled for medical reasons. In addition, the sponsor retains the right to end the study for medical-scientific or GCP-relevant reasons. In case of premature termination the investigators, IRB/IECs and Regulatory Authorities will be informed by the Study Manager. As required by local law, current safety-relevant information will be provided to the IEC / IRB and the regulatory authorities by the sponsor. The sponsor will also inform all investigators about relevant safety events according to the applicable regulations.

11.2 Subject Information and Consent

All relevant information on the study will be summarized in the subject consent form and additionally as required by the investigator's institution in an integrated subject information and consent sheet. A sample informed consent form (ICF) is provided as a document separate to this protocol.

Based on this subject ICF, the investigator will explain all relevant aspects of the study to each subject, before her entry into the study (i.e., before examinations and procedures associated with selection for the study are performed).

The investigator will also mention that written approval of the IRB/IEC has been obtained.

Each subject will have ample time and opportunity to ask questions and will be informed about the right to withdraw from the study at any time without any disadvantage and without having to provide reasons for this decision.

Following this informative discussion, the subject will be asked if he/she is willing to sign and personally date a statement of informed consent. Only if the subject voluntarily agrees to sign the ICF and has done so, may he/she enter the study. Additionally, the investigator or his/her designee will personally sign and date the form. The subject will receive a duplicate of the signed and dated form.

The investigator will record in the source documentation the consent process including the time and date of obtaining informed consent.

In the event that informed consent is obtained on the date that baseline study procedures are performed, the study record or subject's clinical record must clearly show that informed consent was obtained prior to these procedures.

The ICF and any other written information provided to subjects will be revised whenever important new information becomes available that may be relevant to the subject's consent, or there is an amendment to the protocol which necessitates a change to the content of the subject information and/or the written ICF. The investigator will inform the subject of changes in a timely manner and will ask the subject to confirm his/her participation in the study by signing the revised ICF. Any revised written ICF and written information must receive the IRB/IEC's approval/favorable opinion in advance of use.

